# 6. A Priori Statistical Methods

## 6.1. Determination of Sample Size

The primary objective of this study is to compare Abemaciclib versus erlotinib with respect to OS in patients with Stage IV NSCLC whose tumors have detectable *KRAS* mutations (specifically, in codons 12 and 13 of the KRAS oncogene) and who have progressed after prior platinum-based therapy and received 1 additional therapy which may include an immune checkpoint inhibitor and/or other anti-cancer therapy; or are not eligible for further chemotherapy

The study will enroll approximately 450 patients in 3:2 randomization (270 patients in the Abemaciclib arm and 180 patients in the erlotinib arm). The final OS analysis will occur when approximately 304 OS events have been observed.

The comparison of the OS distributions between treatment groups will be conducted using a stratified log-rank test adjusted by all stratification factors. Following statistical hypotheses about OS hazard ratio (HR) will be tested for Abemaciclib over erlotinib:

 $H_0$ :  $HR \ge 1$  (Abemaciclib arm not superior to erlotinib arm)

H1: HR < 1 (Abemaciclib arm superior to erlotinib arm)

Assuming an OS HR of 0.72, this sample size yields approximately 80% statistical power to detect superiority of the Abemaciclib arm over erlotinib arm with the use of a 2-sided log-rank test and a type I error of 0.05.

If the true median OS for the erlotinib arm is 6.5 months, then the HR of 0.72 amounts to an approximately 2.5-month improvement in median OS for the Abemaciclib arm under an additional assumption of exponential survival distribution.

# 6.2. Statistical and Analytical Plans

## 6.2.1. General Considerations

Statistical analysis of this study will be the responsibility of Lilly.

All tests of treatment effects will be conducted at a 2-sided alpha level of 0.05, unless otherwise stated. All tests of interactions will be conducted at a 2-sided alpha level of 0.1, and all confidence intervals (CIs) will be given at a 2-sided 95% level, unless otherwise stated. P-values will be rounded at three significant digits. P-values less than 0.001 will be presented as p <0.001.

Any change to the data analysis methods described in the protocol will require an amendment only if it changes a principal feature of the protocol.

Before unblinding of the aggregate database, minor modifications or clarifications to the data analysis methods may be described and justified in the statistical analysis plan (SAP).

Any other change to the data analysis methods described in the protocol, and the justification for making the change, will be described in the clinical study report.

## 6.2.2. Populations

The entered population includes all patients who sign the informed consent document.

The **enrolled or intent-to-treat (ITT)** population includes all randomized patients. The ITT analysis of efficacy data will consider allocation of patients to treatment groups as randomized and not by actual treatment received. This population will be used for all baseline, efficacy, and health economics analyses.

**Safety population** will include all randomized patients who received any quantity of study treatment, regardless of their eligibility for the study. The safety evaluation will be performed based on the first dose of study treatment a patient actually received, regardless of the arm to which he or she was randomized. The safety population will be used for all dosing/exposure, safety, and resource utilization analyses.

Pharmacokinetic analyses will be conducted on all patients who have received at least 1 dose of Abemaciclib and have had samples collected.

Pharmacodynamic and/or tailoring biomarker analyses will be based on the subset of patients from the above populations from whom a valid assay result (according to laboratory guideline) has been obtained.

## 6.2.3. Definitions and Conventions

Study drug refers to Abemaciclib or erlotinib.

**Study treatment** refers to Abemaciclib + best supportive care or erlotinib + best supportive care.

The **date of randomization** is the date the patient was randomly assigned to Abemaciclib + best supportive care or erlotinib + best supportive care using the interactive web response system (IWRS).

The date of first dose is the date of the first dose of study drug.

The **baseline value of a safety assessment** is the last value observed prior to the first dose of study drug.

The **baseline value of an efficacy assessment** is the last value observed prior to the date of randomization. If a patient's first assessment occurs after randomization but prior to the first dose, this assessment will be used as the baseline.

The study day of a safety event or assessment will be calculated as:

- the difference between the date of the event or assessment and the date of first dose plus 1 for all events or assessments occurring on or after the day of first dose. For example, if an event occurs on 08JUN2014 and the date of first dose was 06JUN2014, the study day of the event is 3.
- the difference between the date of the event or assessment and the date of first dose for all events or assessments occurring before the day of first dose. For example, if an event occurs on 05JUN2014 and the date of first dose was 06JUN2014, the study day of the event is -1.

The study day of an efficacy event or assessment will be calculated as:

- the difference between the date of the event or assessment and the date of randomization plus 1 for all events or assessments occurring on or after the date of randomization.
- the difference between the date of the event or assessment and the date of randomization for all events or assessments occurring before the date of randomization.

One **month** is defined as 365/12 days.

Unless otherwise noted, **summaries of continuous variables** will include a mean, median, standard deviation, minimum, and maximum.

Unless otherwise noted, **summaries of categorical variables** will include the frequency and percentage (relative to the population being analyzed) of each category.

# 6.2.4. Handling of Dropouts or Missing Data

With the exception of dates, missing data will not be imputed. The method of imputation for any dates that are imputed is described in the relevant section.

# 6.2.5. Patient Disposition

A detailed description of patient disposition will be provided. It will include a summary of the number and percentage of patients entered into the study, enrolled in the study, and treated (including number of patients still on treatment as of the data-inclusion cutoff date) as well as number and percentage of patients completing the study, or discontinuing (overall and by reason for discontinuation).

A summary of all important protocol deviations will be provided.

# 6.2.6. Baseline Demographics and Patient Characteristics

Patient demographics including age, sex, screening height and weight, screening body mass index, and smoking status will be reported using descriptive statistics.

Baseline disease characteristics will be summarized by presenting frequency counts and percentages for pathological diagnosis (histological or cytological), disease stage, or performance status.

Patient preexisting condition, historical illness, and prior chemotherapy (including both cytotoxic and targeted agents) will be summarized by treatment arm.

## 6.2.7. Prior and Post Discontinuation Therapies

Prior Therapies: Prior radiotherapy, surgery, and systemic therapy will be summarized. Prior radiotherapy and surgery will be categorized by reason for regimen. Prior systemic therapies will be categorized by reason for regimen ([neo]adjuvant therapy or therapy for locally advanced or metastatic disease), number of regimens for locally advanced or metastatic disease and specific therapy. Frequency of each specific therapy will be tabulated within each reason for therapy.

Prior immunotherapy will be categorized by time on therapy (<4 months or >=4 months). For patients who had one prior chemotherapy based on eCRF, reason for patient being not eligible for further chemotherapy will be summarized by study treatment arms.

Post Discontinuation Therapies: The numbers and percentages of patients reporting postdiscontinuation therapies will be provided overall, by type of therapy (surgery, radiotherapy, or systemic therapy), and by drug name.

### 6.2.8. Treatment Compliance

The number of dose omissions, reductions, and delays, cycles received, and dose intensity will be summarized for all treated patients per treatment arm.

Treatment compliance information for Abemaciclib or erlotinib will be collected through capsule (Abemaciclib) or tablet (erlotinib) counts at each tumor assessment visit. The estimate of percent compliance will be given by:

Percent Compliance =  $\frac{\text{Actual cumulative dose taken}}{\text{Expected cumulative dose to be taken}} \times 100$ 

The actual cumulative dose taken will be determined based on counting the number of capsules returned at each visit and subtracting that number from the number of capsules dispensed. The expected cumulative dose to be taken will be determined based on the assigned dose and taking into account any dose reductions or omissions.

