# 9.4. Selection and Timing of Doses

Abemaciclib will be taken orally every 12 (±approximately 2) hours on Days 1 through 28 of a 28-day cycle, for a total of 56 doses per cycle. On Cycle 1 Day 1, only one 200-mg dose of abemaciclib will be taken. Chronic oral administration of abemaciclib approximately every 12 hours will be initiated on Cycle 1 Day 2 and continue throughout every cycle. During all cycles, abemaciclib should be taken at approximately the same times each day. If a patient misses or vomits a dose, that dose should be omitted.

Erlotinib will be taken orally once daily (approximately every 24 hours) on Days 1 through 28 of a 28-day cycle, for a total of 28 doses per cycle. During all cycles, erlotinib should be taken at approximately the same time each day. If a patient misses or vomits a dose, that dose should be omitted.

A cycle is defined as the planned treatment interval of 28 days plus any subsequent delay prior to the start of the next cycle. A delay of a cycle due to holidays, weekends, bad weather, or other unforeseen circumstances will be permitted up to 7 days and not counted as a protocol deviation. Abemaciclib will be dispensed for 56 doses (28-day supply). Erlotinib will be dispensed with a 30 day supply, but only 28 doses should be taken per cycle.

A patient may continue to receive study drug until he or she meets 1 or more of the specified reasons for discontinuation (as described in Section 7.3.1).

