# 9.7. Treatment Compliance

Patient compliance with study drug will be assessed at each visit. Compliance will be assessed by counting returned tablets/capsules. Patients may use a diary to record study drug intake.

Patients who are significantly noncompliant will be discontinued from the study. Unless required secondary to toxicity, a patient will be considered significantly noncompliant if he or she misses 8 or more consecutive days of study drug (full doses), or more than 25% of the cumulative days of study drug (full doses) during a cycle. Persistent noncompliance may be a reason for discontinuation from study therapy. Similarly, a patient will be considered significantly noncompliant if he or she is judged by the investigator to have intentionally or

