# 12.2.5. Treatment Compliance

The number of dose omissions, reductions, and delays, cycles received, and dose intensity will be summarized for all treated patients per treatment arm.

Treatment compliance information for abemaciclib or erlotinib will be collected through capsule (abemaciclib) or tablet (erlotinib) counts at each tumor assessment visit. The estimate of percent compliance will be given by:

Percent Compliance =  $\frac{\text{Actual cumulative dose taken}}{\text{Expected cumulative dose to be taken}} \times 100$ 

The actual cumulative dose taken will be determined based on counting the number of capsules returned at each visit and subtracting that number from the number of capsules dispensed. The

expected cumulative dose to be taken will be determined based on the assigned dose and taking into account any dose reductions or omissions.

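### Read literally, percent compliance removes missed doses from the expected dose, so it stays at 100% however many doses a patient misses, and vomited doses can push it above 100%

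*SAP*

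**What the plan says.** The compliance formula is the same in SAP 6.2.8 and Protocol 12.2.5: actual cumulative dose over expected cumulative dose, times 100.

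- **Numerator.** It is obtained by "counting the number of capsules returned at each visit and subtracting that number from the number of capsules dispensed".
- **Denominator.** SAP 6.2.8 starts from the assigned dose, "taking into account any dose reductions or omissions". Protocol 12.2.5 has the same rule. Neither document says which omissions qualify.
- **Missed doses.** Protocol 9.4, for both drugs: "If a patient misses or vomits a dose, that dose should be omitted".
- **Directed omissions.** Protocol 9.4.2.2.1 and 9.4.2.2.2 use the same word for doses withheld for tolerability or toxicity.
- **Timing.** The compliance sections first refer to "tablet (erlotinib) counts at each tumor assessment visit", then describe returns as counted at each visit. Protocol 9.7 also assesses compliance at each visit.
- **Dose intensity.** SAP 6.2.14.1 divides the total dose taken by the full assigned dose, 11200 mg per cycle for abemaciclib and 4200 mg for erlotinib, and separately summarises omissions with their reasons.

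**The concern.** A compliance ratio compares what the patient took with what the patient was meant to take. A dose withheld on instruction was not meant to be taken, so removing it from the denominator is sensible. A dose the patient forgot was meant to be taken and should stay. The plan's wording does not separate the two, and the protocol attaches the word for the first kind to the second.

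If the rule is programmed as it reads, the ratio is insensitive to the behaviour it is named for. A compliance table near 100% in both arms would then say nothing about adherence to two self-administered oral drugs. Protocol 9.7 already draws the needed distinction, since it excepts doses missed because of toxicity when it judges a patient noncompliant. The formula does not carry that exception over.

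**Working it through.** **Inputs.** Abemaciclib 200 mg, 56 doses per cycle; erlotinib 150 mg, 28 doses per cycle (Protocol 9.1 and 9.4). In Cycle 1 abemaciclib has a single dose on Day 1, so 1 + 27 × 2 = 55 are scheduled; the examples use a later cycle.

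**The plan's own figures.** 200 × 2 × 28 = 11200 mg and 150 × 28 = 4200 mg. Both match SAP 6.2.14.1.

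**Formulas.** Let N be scheduled doses, m doses missed by the patient and t doses withheld for toxicity. All doses are at the full level and all untaken capsules are returned.

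- Literal reading: (N − t − m) / (N − t − m)
- Only directed omissions removed: (N − t − m) / (N − t)
- Dose intensity: (N − t − m) / N

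The first equals 1 for any m below N − t.

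| Case | Literal | Directed only | Dose intensity |
|---|---|---|---|
| Abemaciclib, 6 of 56 missed | 50/50 = 100% | 50/56 = 89.3% | 89.3% |
| Abemaciclib, 15 of 56 missed | 41/41 = 100% | 41/56 = 73.2% | 73.2% |
| Abemaciclib, 28 of 56 missed | 28/28 = 100% | 28/56 = 50.0% | 50.0% |
| Abemaciclib, 7 withheld for toxicity and 7 missed | 42/42 = 100% | 42/49 = 85.7% | 42/56 = 75.0% |
| Erlotinib, 7 of 28 missed | 21/21 = 100% | 21/28 = 75.0% | 75.0% |

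**Vomited doses.** A vomited capsule is not returned, so the pill count treats it as taken, while Protocol 9.4 labels the dose omitted. With 14 of 56 vomited and none missed, the literal reading gives 56/(56 − 14) = 56/42 = 133%. Treating them alike on both sides gives 56/56 or 42/42, each 100%.

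**What dose intensity adds.** It shows the shortfall in every missed-dose case above but pools causes. A fully adherent patient on 150 mg for a whole cycle has 150 × 56 = 8400 mg, and 8400/11200 = 75%. A patient on 200 mg who misses 14 doses has 200 × 42 = 8400 mg, also 75%. On the literal reading both have 100% compliance, so the two ratios together do not separate them; the summary of reasons for omission can.

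**The case against.** The strongest reply is that the literal reading is not the intended one. The sentence in Protocol 9.4 is a dosing instruction, meaning that a lost dose is not made up. It does not define an analysis term. Elsewhere omission mostly means a managed event, the formula pairs omissions with reductions, and Protocol 9.4.2.2.2 wants reductions documented so that compliance can be determined. On that view only prescribed changes lower the expected dose, and the patient missing 15 of 56 shows 73%. This is a fair reading, and it stands as a reason to call the defect an ambiguity that can produce a wrong figure. It does not remove the point, because neither document states that limit and the text says *any*.

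It is also true that the shortfall is visible elsewhere, as the dose-intensity column shows, and that SAP 6.2.8 reports omission counts beside the percentage.

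A reader might go further in four ways that the documents do not support:

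- **That per-cycle figures are unobtainable** because counts are made only at tumor assessments, every other cycle from Cycle 3. The same section counts returns at each visit, Protocol 9.7 does likewise, and SAP 6.2.14.1 summarises pill-count exposure by cycle. The wording is inconsistent, no more.
- **That the discontinuation rule fails.** Protocol 9.7 sets a limit of 8 or more consecutive days, "or more than 25% of the cumulative days of study drug (full doses) during a cycle". It is an operational rule counted in days, and neither document says the percentage feeds it.
- **That interpretation of overall survival is compromised.** No efficacy analysis uses percent compliance, and under-dosing is shown by dose intensity.
- **That erlotinib supply breaks the formula.** Protocol 9.4 says "Erlotinib will be dispensed with a 30 day supply, but only 28 doses should be taken per cycle", so two unreturned spares would read 30/28 = 107%. But Protocol 9.1 requires unused drug to be returned. Unreturned tablets are an ordinary limit of pill counts.

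**Conclusion.** The point holds in a limited form. Applied as written, percent compliance is fixed at 100% for any number of missed doses: 100% instead of 73% with 15 of 56 missed, and instead of 50% with 28 missed. It can reach 133% with 14 vomited. This rests on three assumptions: that taking omissions into account means subtracting them, which is the only workable way to apply them to an expected dose; that missed doses are recorded as omissions, as Protocol 9.4 labels them; and that unused capsules are returned. If the analysts subtract only directed omissions, missed doses are handled correctly, but the plan does not tell them to.

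The consequence is an uninformative or misleading entry in one descriptive table. The primary analysis, the analysis populations and the dose-intensity summary are unaffected. This is a clarification worth making, not a threat to the trial's conclusions.

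**What to change.** In SAP 6.2.8:

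1. State that the expected dose is lowered only for investigator-directed or toxicity-related holds and reductions, and that doses missed by the patient remain expected.
2. State one rule for vomited doses, applied to both numerator and denominator. Counting them as both taken and expected fits the pill count and needs no extra data.
3. Replace the reference to counts at tumor assessment visits with counts at each visit, so that it agrees with the rest of the section and with Protocol 9.7.

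Protocol 12.2.5 carries the same text. Protocol 12.2.1 lets the SAP clarify analysis methods before the aggregate data are unblinded, so a SAP clarification should suffice up to then; after that, the change and its reason belong in the study report. Dosing and dispensing instructions need no change.

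The cost is a few sentences of SAP text, some reprogramming and a less favourable compliance figure. Little or no new data should be needed, because SAP 6.2.14.1 already plans a summary of reasons for omission. This assumes that the recorded reasons separate patient-missed doses from directed ones.

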## 6.2.9. Concomitant Therapy

Concomitant medication will be summarized by treatment arm in a frequency table listing the terms recorded on the electronic clinical (case) report form (eCRF).

## 6.2.10. Efficacy Analyses

### 6.2.10.1. Stratification Factors

The stratification factors for the analysis are: number of prior chemotherapy regimens (1 versus 2), performance status (ECOG 0 versus 1), gender (male versus female), and *KRAS* mutation (G12C versus all others).

The stratification factors are captured in the IWRS and eCRFs. KRAS mutation status is also captured through central laboratory system. Unless otherwise stated, all stratification analyses will be based on the stratification factors per IWRS.

#### 6.2.10.2. Primary Efficacy Endpoint

The primary efficacy endpoint in JPBK is OS.

**Overall Survival (OS)** time is defined as the time from the date of randomization (Day 1) to the date of death from any cause. For each patient who is not known to have died as of the data-inclusion cutoff date for a particular analysis, OS will be censored for that analysis at the date of last contact prior to the data inclusion cutoff date.

The comparison of the OS distributions between treatment groups will be conducted using a stratified log-rank test with the following stratification variables: number of prior chemotherapy regimens (1 versus 2), ECOG PS (0 versus 1), gender (male versus female), and *KRAS* mutation (G12C versus all others). The sources of the stratification factors will be IWRS.

The Kaplan-Meier method (Kaplan and Meier 1958) will be used to estimate the OS survival curves as well as survival rates at 3, 6, 9, and 12 months for each treatment group. These rates will be compared based on a normal approximation for the difference between the arms. The Cox proportional hazard model (Cox 1972) with treatment as a factor, stratified by the stratification factors used in the randomization (as per the primary analysis) will be used to estimate the HR and corresponding 95% CI.

#### 6.2.10.3. Secondary Efficacy Endpoints

**Progression-free survival (PFS)** time is defined as the time from the date of randomization (Day 1) to the date of investigator-determined objective progression as defined by RECIST 1.1 (Eisenhauer et al. 2009) or the date of death due to any cause, whichever is earlier. Patients who have neither progressed nor died will be censored at the day of their last radiographic tumor assessment, if available or date of randomization if no post initiation (i.e., post baseline) radiographic assessment is available. The detailed censoring rules are described in the Table JPBK.6.1.

The statistical comparison of PFS between treatment groups will be conducted using the same methods for OS as described in Section 6.2.10.2.

Table JPBK.6.1.	Rules for Determining Date of Progression or Censor for
	Progression-Free Survival

	Situation	Date of Progression or Censor	Outcome
1	No baseline tumor assessments	Date of Randomization	Censored
2	No post baseline assessments and no death	Date of Randomization	Censored
3	No documented progression and no death (with a post-baseline tumor assessment)	Date of last adequate tumor assessment	Censored
4	Patient lost to follow-up (or withdrew consent from study participation) before documented progression or death	Date of last adequate tumor assessment	Censored
5	Documented progression	Date of documented progression. If a tumor assessment was done on multiple days, use the earliest date for that visit.	Progressed
6	Death without documented progression	Date of death	Progressed
7	Death or documented progression immediately after missed ≥2 consecutive post-baseline tumor assessment visits	Date of last adequate tumor assessment before missed assessments or date of randomization, whichever is later	Censored

Note: PFS and associated outcome is determined by the earliest of the dates above, if more than one situation applies

Other secondary efficacy measures include response rate as defined by RECIST 1.1 (Eisenhauer et al. 2009).

Best overall response (BOR) will be derived to encompass all tumor assessments (according to RECIST v1.1) from baseline until the earliest of objective progression or start of new anticancer therapy. Any responses observed after objective progression or the start of new anticancer therapy are excluded from the determination of best response. Each patient's BOR will categorized as complete response (CR), partial response (PR), stable disease (SD), progressive disease (PD), or not evaluable (NE).

Overall Response Rate (ORR) is defined as the proportion of patients with BOR of CR or PR (according to RECIST v1.1). Disease control rate (DCR) is defined as the proportion of patients with BOR of CR, PR or SD (according to RECIST v1.1).

Point estimates and 95% confidence intervals (using the normal approximation to the binomial) will be calculated for ORR and DCR by treatment arm. Stratified tests comparing these rates between treatment arms will be conducted using a Cochran-Mantel-Haenszel (CMH) test adjusted by all stratification factors.

Duration of response (DoR) will be presented for responders (patients with a BOR of CR or PR according to RECIST 1.1). DoR is defined as the time from the date of the first evidence of CR or PR to the date of investigator-determined objective progression or the date of death due to any cause, whichever is earlier. DoR will be censored according to the same rules as PFS (presented in Table JPBK.6.1). The median duration of response will be summarized using K-M

techniques. The statistical comparison of DoR between treatment groups will be conducted using unstratified log-rank test and HR will be estimated using an unstratified Cox model with only the treatment factor in the model.

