# Table JPBK.12.1.Rules for Determining Date of Progression or Censor for
Progression-Free Survival

Note: Progression-free survival and associated outcome is determined by the earliest of the dates above, if more than 1 situation applies.

The statistical comparison of PFS between treatment groups will be conducted using the same methods for OS as described in Section 12.2.6.

The objective response rate of each treatment arm will be calculated as defined by RECIST v1.1. All rates will be compared between treatment arms based on a normal approximation for the difference between the rates.

Details of the statistical methods for analyzing efficacy outcomes are described in the SAP.

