# 12.2.10. Biomarker Analyses

### 12.2.10.1. KRAS Mutation Assessment

Concordance (agreement) analysis will be performed on samples with valid *KRAS* status (mutation positive and mutation negative) using both the investigational assay and the reference method (Sanger sequencing). Measures of agreement between the investigational *KRAS* assay and the reference method, including positive percent agreement, negative percent agreement, and overall percent agreement, and their corresponding exact 2-sided 95% CIs, will be estimated for the overall mutation status; that is, mutation detected or not detected for the 7 mutations of *KRAS* gene. A secondary agreement analysis between the investigational *KRAS* assay and the reference method will be performed for each of the tumor tissue sample types (surgical resection, fine needle aspirate and core needle biopsy). The data will also be summarized for each of the 7 *KRAS* mutations separately.

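### The per-arm 95% intervals for overall response rate use the normal approximation, which falls short of 95% if the true response rate is below about 5%

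*SAP*

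**What the plan says.** SAP 6.2.10.3 (Secondary Efficacy Endpoints) reads: "Point estimates and 95% confidence intervals (using the normal approximation to the binomial) will be calculated for ORR and DCR by treatment arm". The words at issue are "using the normal approximation to the binomial". The same section defines the endpoint: "Overall Response Rate (ORR) is defined as the proportion of patients with BOR of CR or PR". SAP 6.2.1 sets the level: "all confidence intervals (CIs) will be given at a 2-sided 95% level, unless otherwise stated". The denominators are all randomized patients, since SAP 6.2.2 says of the ITT population: "This population will be used for all baseline, efficacy, and health economics analyses". SAP 6.1 plans "270 patients in the Abemaciclib arm and 180 patients in the erlotinib arm".

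No section gives an exact or score alternative, or a rule for an arm with very few or no responders.

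For the comparison between arms, SAP 6.2.10.3 uses a Cochran-Mantel-Haenszel test adjusted for the stratification factors. That test does not use the per-arm intervals. Protocol 12.2.7 describes the comparison differently: "All rates will be compared between treatment arms based on a normal approximation for the difference between the rates".

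For a different purpose, agreement between the KRAS assay and the reference method, protocol 12.2.10.1 asks for measures of agreement "and their corresponding exact 2-sided 95% CIs".

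**The concern.** The normal-approximation (Wald) interval is unreliable when the expected number of events is small. It is symmetric around an estimate whose distribution is skewed, and its width is estimated from the same few events. A low count therefore gives an interval that is both too low and too narrow. In the extreme it runs below zero or collapses to a single point.

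The documents make a low response rate plausible without giving one:

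- Protocol 7.1 enrolls patients who have progressed after platinum and have had another therapy or are judged ineligible for further standard second-line chemotherapy.
- The protocol Introduction reports a numerically inferior response rate with EGFR inhibitors in KRAS-mutant tumors, without a figure.
- For abemaciclib in KRAS-mutant tumors, the Introduction reports only disease control, 16 of 29 (55.2%).
- Protocol 10.1.4 counts only confirmed responses.

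At stake is the reported precision of one secondary efficacy endpoint. An interval labelled 95% could have a negative limit, have no width, or miss the true rate more often than its label says.

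**Working it through.** **Inputs.** Total 450 patients, 3:2 allocation (SAP 6.1): 450 × 3/5 = 270 and 450 × 2/5 = 180, matching the SAP's arms. Level 95% two-sided, z = 1.96. True ORR: not in the documents, so a range is assumed. The nominal 95% is the only figure the plan gives on this point; it states no ORR, ORR precision or ORR power to reproduce.

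**Step 1: the interval.** With x responders among n patients and p̂ = x/n, the Wald interval is p̂ ± 1.96 × √(p̂(1 − p̂)/n).

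- n = 180, x = 3: p̂ = 1.67%, half-width 1.87 points, so −0.20% to 3.54%. Wilson gives 0.57% to 4.78%; Clopper-Pearson 0.35% to 4.79%.
- n = 180, x = 0: the half-width is zero, so 0% to 0%. Clopper-Pearson gives 0% to 2.03%.
- n = 270, x = 3: −0.14% to 2.36%. Wilson gives 0.38% to 3.22%; Clopper-Pearson 0.23% to 3.21%.
- n = 270, x = 0: 0% to 0%. Clopper-Pearson gives 0% to 1.36%.

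In both arms the lower limit is negative for x = 1, 2 or 3 and positive from x = 4 (0.07% at n = 180, 0.04% at n = 270).

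**Step 2: exact coverage.** For a true rate p, coverage is the sum of the binomial probabilities P(X = x | n, p) over every x whose interval contains p.

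| True ORR | Wald, n=180 | Wilson, n=180 | Clopper-Pearson, n=180 | Wald, n=270 | Wilson, n=270 | Clopper-Pearson, n=270 |
|---|---|---|---|---|---|---|
| 1% | 83.4% | 96.4% | 99.0% | 93.2% | 94.4% | 98.0% |
| 2% | 87.3% | 97.1% | 98.9% | 90.4% | 94.9% | 97.4% |
| 3% | 90.0% | 95.0% | 97.5% | 90.1% | 95.3% | 97.1% |
| 4% | 92.6% | 94.7% | 96.3% | 91.1% | 95.9% | 97.1% |
| 5% | 94.0% | 94.4% | 96.2% | 91.7% | 95.2% | 96.5% |
| 6% | 90.7% | 96.1% | 96.1% | 92.3% | 94.7% | 96.1% |

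Coverage moves in jumps because responder counts are whole numbers, so averages over bands are more informative than single rates. Mean Wald coverage:

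| True ORR band | n=180 | n=270 |
|---|---|---|
| 1–3% | 89.0% | 90.5% |
| 3–5% | 92.1% | 93.0% |
| 5–10% | 93.4% | 93.9% |
| 10–20% | 94.3% | 94.5% |

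**Step 3: direction of the misses.** At n = 180 and a true rate of 2%, the interval lies wholly below the truth in 12.3% of trials and wholly above it in 0.4%. At 1% the split is 16.4% to 0.2%.

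**Step 4: what drives the 1% row.** The probability of no responders at n = 180 is 0.99^180 = 16.4%, nearly all of the 16.6% miss. At n = 270 it is 0.99^270 = 6.6%, out of a 6.8% miss. So at 1% the shortfall is almost entirely the 0% to 0% interval.

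**Step 5: how often a limit is negative.** This is P(1 ≤ X ≤ 3) = P(X ≤ 3) − P(X = 0).

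| True ORR | n=180 | n=270 |
|---|---|---|
| 1% | 89.2% − 16.4% = 73% (unrounded 72.9%) | 71.4% − 6.6% = 65% |
| 2% | 51.4% − 2.6% = 49% | 21.0% − 0.4% = 21% |
| 3% | 20.9% − 0.4% = 20.5% | 3.8% − 0.03% = 4% |

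**Step 6: disease control rate.** At the Phase 1 rates in the protocol Introduction (37.5% and 55.2%), Wald coverage is 94.5–95.0% in both arm sizes. There is no defect there.

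**The case against.** **The low rate is assumed.** Neither document gives an ORR for either arm. At true rates above 10% the Wald interval is adequate at these sample sizes. This stands, and it makes the point conditional. It does not remove it, because a prespecified method should work across the plausible range and the alternatives do so at little cost.

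**Nothing is decided by these intervals.** Overall survival is the sole primary endpoint, ORR is compared by the stratified test, and no alpha or sample-size rule uses the per-arm intervals. This stands and keeps the point minor.

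**The protocol already allows a substitute.** Section 12.2.1 says that method assumptions will be checked and that alternatives may be used if they are violated. This helps in part, but the wording is permissive and names no trigger or replacement.

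**Stronger readings that the documents do not support.**

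- A reader might infer that the intervals miss three times as often as labelled. That ratio (16.6% against 5%) belongs to one case, 180 patients at a 1% rate, and comes from the zero-responder outcome, which would be obvious in a table. At 2–3% in that arm the ratio is about 2 to 2.5 (12.7% and 10.0% against 5%).
- A reader might extend the defect to disease control rate, which Step 6 does not support.
- A reader might see the exact intervals for KRAS agreement as an internal contradiction. They serve assay agreement, a different purpose, and show only that the plan already uses such intervals.
- A reader might conclude that the between-arm comparison is invalid. The difference between protocol 12.2.7 and the SAP on that test is a separate matter, and nothing here shows a defect in either method.

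**Conclusion.** The point holds in a limited form and is minor. If the true ORR is below about 5% in an arm, the SAP's intervals average about 89–93% coverage instead of 95%, and most misses come from lying too low. The shortfall is modest at 5–10% and small above 10%.

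Negative lower limits need one to three responders. They are realistic only at true rates of roughly 4% or less with 180 patients, or 3% or less with 270. An arm with no responders would be reported as 0% to 0%.

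The coverage figures are exact given the planned arm sizes. The low response rate is the one assumption, and the documents neither confirm nor exclude it. The overall survival analysis and the stratified ORR test do not depend on these intervals.

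**What to change.** In SAP 6.2.10.3, replace the normal approximation with Wilson or Clopper-Pearson 95% intervals for ORR by arm. Either one removes the negative and zero-width intervals. Over true rates of 1–20%, the lowest coverage is about 93% for Wilson and about 95% for Clopper-Pearson. Disease control rate may follow for consistency of presentation, though no defect is shown there. No change to the between-arm test is needed on this account.

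The cost is one sentence in the SAP and a standard software option. The intervals become slightly wider: at 8 responders of 180, Wald runs from 1.43% to 7.46%, Wilson from 2.27% to 8.52% and Clopper-Pearson from 1.94% to 8.57%.
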